10.3 Assessment of adverse events

All adverse events must be assessed for seriousness. SAEs occurring between the date of consent and 30 days post treatment must be assessed for causality,

expectedness and severity and notified to the Sponsor. This is the responsibility of the CI or designee.

Seriousness

AEs should be assessed for seriousness as per the definitions in section 10.1; those meeting the criteria for an SAE are subject to expedited reporting to the sponsor.

Assessment of causality

SAEs must be assessed for their causality i.e. does the event have a reasonable causal relationship with the trial medication.

Assessment of expectedness

If an SAE is considered to be related (possibly, probably or definitely) to the study medication, an assessment should be made of the expectedness of the reaction i.e. is the reaction a recognised adverse effect of the medication.

The expectedness of an adverse reaction must be assessed against the Reference Safety Information (RSI) i.e. the list of expected reactions detailed in the Summary of Product Characteristics (SmPC) for the Investigational Medicinal Product approved during Clinical Trial Authorisation process.

Expected: consistent with the relevant product information documented in the RSI.

Unexpected: not consistent with the relevant product information documented in the RSI.

Assessment of Severity

This should be assessed and described using the following categories:

- Mild-awareness of event but easily tolerated
- Moderate-discomfort enough to cause some interference with usual activity
- Severe-inability to carry out usual activity.

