6.8 Monitoring of potential side effects

6.8.1 Management of nephrotoxicity

Both study drugs are potentially nephrotoxic and close monitoring of renal function (serum urea, creatinine and electrolytes) for the duration of the trial will be mandatory. This will include baseline measurements along with measurements prior to and after the introduction of the study drug and after any dose change. Measurements will also be taken at regular intervals for the duration of the trial. Alert ranges for laboratory and other test abnormalities are included in Appendix 1. Additional measurements will be used if clinically indicated. All results will be reviewed in a timely manner when available and if action is required this will be expedited immediately. Each patient will have their renal function (along liver function tests) checked at the following time-points:

- Visit 1: Week 0 (pre-randomisation)
- Visit 2: Week 1 (± 3 days)
- Visit 3: Week 2 (± 3 days)
- Visit 4: Week 4 (± 3 days - pre up-titration of study drug)
- Visit 5: Week 5 (± 3 days - 1 week post up-titration of study drug)
- Visit 6: Week 14 (± 7 days)
- Visit 7: Week 26 (± 7 days)
- Visit 8: Week 39 (± 7 days)
- Visit 9: Week 52 (± 7 days)

If, at any time after randomisation, eGFR decreases by $\geq 25\%$ from baseline (or if serum creatinine concentration increases to $221\text{ }\mu\text{mol/L}$), potentially reversible cases of renal dysfunction will be sought including: non-steroidal anti-inflammatory drug

intake, antibiotics, or other nephrotoxic medications; hypovolaemia; and urinary tract infection. If felt to be appropriate, the study drug dose can be reduced and continued with regular monitoring of renal function. If a patient's eGFR decreases by $\geq 40\%$ from baseline (or if serum creatinine concentration rises above 265 $\mu\text{mol/L}$, then this is an indication to stop the study drug. Thereafter, serum creatinine assessments will have to be repeated at least weekly until levels return to acceptable values. Re-challenging with the study drug at a lower dose level will be considered if deemed clinically safe to do so.

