6.8.2 Management of hyperkalaemia

Patients with elevated potassium value will be managed according to the corrective actions outlined below.

Serum potassium > 5.3 and less than or equal to 5.5 mmol/L

- Confirm potassium concentration in a non-haemolysed sample
- Reinforce low potassium diet and restriction of food/drinks with high potassium content
 - (e.g. orange juice, melon, bananas, low-salt substitutes etc.)
- Review medical regimen (including dietary supplements and over-the-counter medications) for agents known to cause hyperkalaemia. Consider reduction in dose or discontinuation of these agents:
 - Potassium-sparing diuretics (e.g. amiloride and triamterene) including in combination products with thiazide or loop diuretics
 - Potassium supplements, e.g., potassium chloride
 - Salt substitutes
 - Non-steroidal anti-inflammatory drugs (NSAIDs)
 - Cyclo-oxygenase-2 (COX-2) inhibitors
 - Trimethoprim and trimethoprim-containing combination products
 - Herbal Supplements: For example, Noni juice, alfalfa (*Medicago sativa*), dandelion (*Taraxacum officinale*), horsetail (*Equisetum arvense*), nettle (*Urtica dioica*), milkweed, lily of the valley, Siberian ginseng, hawthorn berries
- Repeat serum potassium measurement within 3 to 5 days
- If serum potassium remains > 5.3 and ≤ 5.5 mmol/L, regularly monitor serum potassium levels to ensure stability (suggested once monthly)
- Consider down-titration of study medication, according to investigator's medical judgment.

Serum potassium > 5.5 and < 6.0 mmol/L

- Confirm potassium concentration in a non-haemolysed sample
- Consider down-titration or temporarily discontinue study drug according to investigator medical judgment.
- Apply all measures outlined for serum potassium > 5.3 and ≤ 5.5 mmol/L
- Repeat serum potassium measurement after 2-3 days
- If serum potassium < 5.5 mmol/L, consider resumption of study drug at lower dose with repeat potassium within 5 days

Serum potassium greater than or equal to 6.0 mmol/L

- Immediately discontinue study drug

- Confirm potassium concentration in a non-haemolysed sample
- Urgently evaluate patient and treat hyperkalaemia as clinically indicated
- Apply all measures outlined for serum potassium > 5.3 and < 6.0 mmol/L
- Resumption of study drug will be decided on a case-by-case basis by the investigators.

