2.5.2. ADVERSE EVENTS OF INTEREST

Adverse events of interest include:

- Worsening renal function or acute kidney injury
- Hyperkalaemia
- Symptomatic hypotension
- Symptomatic hypotension with systolic BP <90mmHg
- Angioedema
- Cough

The number and percentage of subjects experiencing one of the adverse events of interest listed will be summarised overall and by randomised treatment group. The Fisher's Exact test will be used to assess whether there is a statistical difference between number of subjects experiencing each event between treatment groups. The following event details will also be summarised and compared between groups: seriousness criteria, severity, relationship to study drug and details of action taken. Full details of these events are provided in section 10.2 of the study protocol.

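### SAP 2.5.2 compares severity of hyperkalaemia and renal events between arms, but the only severity scale is symptom-based and required only for SAEs

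*Protocol*

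**What the plan says.** Protocol 10.3 defines severity in three steps: "Mild-awareness of event but easily tolerated"; "Moderate-discomfort enough to cause some interference with usual activity"; "Severe-inability to carry out usual activity". No laboratory value enters any of them.

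The same section limits who must be graded. Every adverse event is assessed for seriousness, but the fuller assessment is for serious events: "SAEs occurring between the date of consent and 30 days post treatment must be assessed for causality", and the sentence goes on to "expectedness and severity and notified to the Sponsor". Protocol 10.2 lists the reactions collected in the eCRF at follow-up visits (hypotension, renal events, hyperkalaemia, angioedema). For these it names seriousness and current outcome as the data to be collected; it does not name severity.

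SAP 2.5.2 lists six adverse events of interest. It plans to summarise and compare between arms "seriousness criteria, severity, relationship to study drug and details of action taken". It gives no definition of severity and points to protocol 10.2 for details of the events.

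Protocol 6.8 sets laboratory thresholds that apply whether or not the patient has symptoms. Under "Serum potassium greater than or equal to 6.0 mmol/L", 6.8.2 calls for study drug to be stopped at once. In 6.8.1, an eGFR fall of at least 40% or a creatinine above 265 µmol/L is reached and "then this is an indication to stop the study drug".

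**The concern.** Hyperkalaemia and worsening renal function are recognised from blood results. The protocol takes urea and electrolytes at every visit, so many such events could be found in patients who notice nothing. A scale built on what the patient feels or can do has nothing to measure in those cases.

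These are also known risks of the drug classes under test, which is why the plan has stopping thresholds for them. A by-arm severity table for these events should show whether one arm has the worse biochemical disturbances. If the grade is missing or uninformative, the table cannot answer that question, and a reader may take similar columns as evidence of similar severity.

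**Working it through.** The plan gives no figure for this point, so the check sets the sections side by side.

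**Step 1: must these events carry a grade?** Protocol 10.3 requires severity for SAEs. Protocol 10.2 names seriousness and outcome for the listed reactions. SAP 2.5.2 needs severity for all events of interest, serious or not. A non-serious hyperkalaemia or renal event therefore enters a severity comparison without any protocol requirement that its severity be recorded.

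**Step 2: if graded, what can the grade be?** Take a patient without symptoms and apply the wording of 10.3 to each level in 6.8.

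| Level in protocol 6.8 | Consequence stated there | Literal grade under 10.3, no symptoms |
|---|---|---|
| Potassium >5.3 to 5.5 mmol/L | Corrective steps; consider lower dose | At most mild |
| Potassium >5.5 to <6.0 mmol/L | Consider lower dose or temporary stop | At most mild |
| Potassium ≥6.0 mmol/L | Stop drug at once; urgent evaluation | At most mild |
| eGFR fall ≥25%, or creatinine 221 µmol/L | Seek reversible causes; dose may be reduced | At most mild |
| eGFR fall ≥40%, or creatinine above 265 µmol/L | Indication to stop drug | At most mild |

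Moderate needs discomfort and severe needs inability, so neither is open. Strictly, an event that the patient does not notice does not meet mild either, since mild presupposes awareness. Five laboratory levels (three potassium, two renal) thus share at most one grade. Protocol Appendix 1 does not help: its limits are single alert values (potassium up by more than 20%, creatinine up by more than 50%) and are not tied to severity.

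**Step 3: does another planned analysis separate the levels?** SAP 2.5.2 compares incidence by Fisher's exact test, and also seriousness and action taken. SAP 2.2 and 2.5.1 report withdrawal from study medication with reasons. These capture stopping of drug. They do not capture the laboratory level, because action is discretionary in the middle potassium band and at the 25% eGFR level, so one action can follow quite different values. SAP 2.5 covers withdrawal, adverse events of interest and SAEs; it specifies no summary of potassium, creatinine or eGFR after baseline.

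**Step 4: how much of the safety plan is affected?** Two of the six event types in SAP 2.5.2 are defined by laboratory values: 2/6, or one third of the list. SAP 2.5.3 also summarises SAE severity by arm, so a serious but symptom-free laboratory event meets the same scale there.

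**The case against.** Four arguments on the other side have weight.

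- A reader might infer that a symptom-free event that stops study drug is graded mild. The documents do not say so. Severity is required only for SAEs, unfelt events do not fit the wording of mild, and protocol 10.6 leaves severity to the investigator's medical judgement. This stands: mild is the highest literal grade, not a documented outcome. Judgement does not fully repair the gap, because 10.3 directs it into these three categories. If investigators go outside them, grading follows no stated rule.
- A reader might also infer that the whole safety comparison would mislead. That goes too far. Incidence, seriousness, action taken and withdrawal are reported by other routes, so an excess of drug stops in one arm would be visible. What remains is that the severity comparison itself adds nothing for these events, and no planned table shows the values.
- No potassium level is given that makes hyperkalaemia a reportable adverse event. A value of 5.4 mmol/L prompts corrective steps in 6.8.2 yet still meets the up-titration criterion of below 5.5 in Table 4-3, so it may never be reported as an event. This also stands: how many of the five levels appear together in the event table is unknown.
- Thresholds written for management are not severity grades, and rewriting 10.3 would disturb SAE assessment. Accepted. The remedy should be a tabulation beside the scale, not a new scale.

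**Conclusion.** The concern holds in a limited form. SAP 2.5.2 plans a severity comparison for laboratory-defined events using a variable that the protocol does not require for non-serious cases, and that has no laboratory anchor where it is required. For symptom-free events the comparison cannot distinguish those at a stop threshold from lesser ones. It affects 2 of the 6 adverse events of interest; the primary endpoint is untouched.

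The number of patients affected cannot be estimated, since the documents give no expected event counts and no share without symptoms. The conclusion rests on the documents alone. If the eCRF has a severity field for all events of interest, the missing-data part falls away, but the lack of an anchor remains. This is an inexpensive change that should be made; it does not threaten the trial's main conclusion.

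**What to change.** 1. In SAP 2.5.2, for these two event types, replace or supplement the severity comparison with a by-arm table of all randomised patients who have a post-baseline value:
   - peak potassium: up to 5.3, >5.3 to 5.5, >5.5 to <6.0, and ≥6.0 mmol/L;
   - largest eGFR fall from baseline: <25%, 25 to <40%, and ≥40%, or the creatinine levels in protocol 6.8.1. State before unblinding which of the two is used.

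   Counting patients by value also avoids reliance on an unstated reporting threshold for hyperkalaemia. A descriptive table is enough.
2. Reconcile protocol 10.2 and 10.3 with SAP 2.5.2 on which events receive a severity grade.
3. Leave the 10.3 scale in place for SAE reporting and for symptomatic events.

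The bands serve tabulation only and change no management rule. The cost is a few lines of wording and two derived variables, from bloods already scheduled at every visit; this assumes that post-baseline results are held in the trial database. The drawback is that peak values depend on when blood was taken and on whether unscheduled results are captured.

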10.4 Reporting to sponsor (Pharmacovigilance Office)

All SAEs arising during the study will be reported by the Principal Investigator (or designee) to the sponsor (PV Office) by completing the trial eCRF as soon as reasonably practicable and in any event within 24 hours of first becoming aware of the event. Any follow up information should also be reported.

In the event that eCRF reporting is not possible, a paper SAE form (CTIMP) can be downloaded from the Glasgow Clinical Trials Unit website: www.glasgowctu.org.

This should be completed and faxed to the PV Office. ([contact]). A copy of the complete form should be placed in the Study Site File. If necessary, a verbal report can be given by contacting the PV Office on [name]

[name]/ [name]. This must be followed up as soon as possible with a written report.

10.5 Reporting to the MHRA and MREC

All SAEs assigned by the PI or delegate and by the CI (on behalf of the sponsor), as both suspected to be related to IMP-treatment and unexpected will be classified as Suspected Unexpected Serious Adverse Reactions (SUSARs). These will be subject to expedited reporting to the Medicines and Healthcare Products Regulatory Agency (MHRA). The Sponsor Pharmacovigilance office will inform the MHRA, the REC and the Sponsor of SUSARs within the required expedited reporting timescales.

- Fatal or life threatening SUSARs: not later than 7 days after the sponsor had information that the case fulfilled the criteria for a fatal or life threatening SUSAR, and any follow up information within a further 8 days.
- All other SUSARs: not later than 15 days after the sponsor had information that the case fulfilled the criteria for a SUSAR.

10.6 Responsibilities

Chief Investigator (CI) / delegate or independent clinical reviewer:

1. Clinical oversight of the safety of patients participating in the trial, including an ongoing review of the risk / benefit.
2. Using medical judgement in confirming PI's assessment of expectedness of SAEs for 'related' SAEs.
3. Immediate review of all SUSARs.
4. Preparing the clinical sections and final sign off of the Development Safety Update Report (DSUR).

Principal Investigator (PI):

1. Checking for AEs and ARs when participants attend for treatment / follow-up.
2. Using medical judgement in assigning seriousness, severity, causality and expectedness using the Reference Safety Information approved for the trial.
3. Ensuring that all SAEs and SARs (including SUSARs) are recorded and reported to the Sponsor within 24 hours of becoming aware of the event and provide further follow-up information as soon as available.
4. Ensuring that SAEs meeting the definition of SAEs of special interest are marked as such.
5. Using medical judgement in assigning expectedness of SAEs for 'related' SAEs.

Sponsor:

1. Central data collection and verification SAEs, SARs and SUSARs according to the trial protocol.

2. Reporting safety information to the CI, delegate or independent clinical reviewer for the ongoing assessment of the risk / benefit according to the Trial Monitoring Plan.
3. Reporting safety information to the independent oversight committees identified for the trial (Trial Steering Committee (TSC)) according to the Trial Monitoring Plan.
4. Expedited reporting of SUSARs to the Competent Authority (MHRA in UK) and REC within required timelines.
5. Notifying Investigators of SUSARs that occur within the trial.
6. Checking for (annually) and notifying PIs of updates to the Reference Safety Information for the trial.
7. Preparing standard tables and other relevant information for the DSUR in collaboration with the CI and ensuring timely submission to the MHRA and REC.

Trial Steering Committee (TSC):

In accordance with the Trial Terms of Reference for the TSC, periodically reviewing safety data and liaising with the CI and TMG regarding safety issues.

10.7 Pregnancy reporting

Pregnancy is not considered an AE or SAE. However, Principal Investigators will report pregnancy information on any female participant or female partner of a male participant who becomes pregnant while participating in the trial to the sponsor within two weeks of first becoming aware of the pregnancy. This report should be provided to the PV office on the Pregnancy Notification Form provide by the sponsor (on www.glasgowctu.org). The subject will also be followed to determine the outcome of the pregnancy. Information on the status of the mother and child will be forwarded by the PI to the PV Office

10.8 Development safety update reports

A Development Safety Update Report (DSUR) will be submitted once a year, or on request, to MHRA and REC until the trial is declared ended. The report will be submitted within 60 days of the anniversary of the issue of the Clinical Trials Authorisation for the trial. The report will be prepared by the sponsor (PV Office) in liaison with the CI and submitted by the sponsor (PV Office).

11 Statistics and data analysis plan

11.1 Sample size

A sample size of 100 patients is proposed. This is based on the calculation that 45 patients per treatment group provides >90% power (α level = 0.05) to detect a difference of 6mL/m² in LVESVI (standard deviation = 7.8mL/m²) and accounting for a discontinuation rate of 10% (lost to follow up, development of heart failure or

death).³⁷ A 6mL/m² difference in LVESVI represents a minimally important difference.

11.2 Planned recruitment rate

Recruitment of 100 patients in 18 months requires a monthly recruitment rate of 5.6 patients/month or 1.4 patients/week. We have previously recruited patients (n=100) in a study with similar inclusion criteria within the time-frame of 12 months.³⁸ Data collected from a pharmacy led “post MI clinic” for patients with LVSD following an MI report a yearly incidence of around 90 patients with an LVEF ≤ 40% and without any evidence of clinical HF (NYHA I). We plan to use the database from these clinics to identify suitable patients as well as recruiting patients newly referred to the clinic following a MI. Recent restructuring of the health services in Glasgow has resulted in the amalgamation of 3 hospitals (Western Infirmary, Southern General and the Victoria Infirmary) into a single site at the Queen Elizabeth University Hospital (QEUH). We plan to base recruitment at this site given its large catchment population of 560,000. We will also recruit patients from QEUH, GRI, RAH, New Victoria Hospital, West Glasgow Ambulatory Care Hospital, Inverclyde Hospital, Vale of Leven Hospital, Wishaw General Hospital, Hairmyres Hospital and Monklands General Hospital via post-myocardial infarction outpatient clinics and general cardiology clinics.

11.3 Statistical analysis

The study will have a comprehensive Statistical Analysis Plan, which will be authored by the Trial Statistician and agreed by the Investigators before the final unblinded analysis. Analysis will be done on an intention-to-treat basis. The Robertson Centre for Biostatistics, functional unit of the Glasgow Clinical Trials Unit, a fully registered UK CRN Clinical Trials Unit, will manage and analyse trial data.

The primary analysis will compare LVESVI at 12 months between randomised groups using a linear regression model, adjusted for baseline LVESVI, and whether or not taking diuretics at baseline. Similar methods will be applied to secondary outcomes. Safety data will be summarised without formal statistical comparison.

12 Data handling

12.1 Randomisation

Randomisation will be in a 1:1 ratio and stratified by LVESVI ≤45mL/m² / >45mL/m² as measured by baseline CMR, and whether or not the patient is being prescribed diuretics at baseline, with the randomisation schedule computer generated by the method of randomised permuted blocks, with random block lengths of 4 and 6. The allocation for each patient will not be known to researchers until the point of randomisation. The full allocation sequence will be stored in a secure area of the Robertson Centre for Biostatistics network, with access restricted to those responsible for maintenance of the randomisation system. Study statisticians will not have access to the allocation schedule until the database has been locked, and all

analysis programs have been validated according to a prespecified statistical validation plan.

12.2 Case Report Forms

A study specific electronic case report form (eCRF) will be used to collect study data. It is the investigator's responsibility to ensure completion and to review and approve all data captured in the eCRF. All data handling procedures will be detailed in a Study Specific Data Management Plan. Data will be validated at the point of entry into the eCRF and at regular intervals during the study. Data discrepancies will be flagged to the investigators and any data changes will be recorded in order to maintain a complete audit trail (reason for change, date change made, who made change).

